10.4.2 RIG vs. SYN023 Comparison by Timepoint

Using GLM procedures in SAS[®], ANOVA will be performed separately on ln-transformed RVNA at Day 1, Day 3, Day 7, Day 14, Day 28, Day 35, Day 42, Day 84, and Day 112 at the alpha level of 0.05. Factors incorporated in the model will include: Vaccine, Conmed, and Vaccine*Conmed. Vaccine, Conmed, and Vaccine*Conmed will be tested against the residual mean square error. In the case of a non-statistically significant Vaccine*Conmed interaction term, the analysis will be rerun excluding this term from the ANOVA model in order to obtain ratios and confidence intervals where appropriate. In the case of statistically significant Vaccine*Conmed interaction term, the analysis will be rerun for each vaccine separately. All sums of squares (Types I, II, III and IV) will be reported. Probability (p) values will be derived from Type III sums of squares. Coefficients of variation (CV%) will be estimated.

Based on pairwise comparisons of the ln-transformed Day 1, Day 3, Day 7, Day 14, Day 28, Day 35, Day 42, Day 84, and Day 112 data, the ratio (RIG/SYN023) of the geometric least-squares means, calculated according to the formula “ $e^{(X-Y)} * 100$ ”, as well as the corresponding 90% and 95% geometric confidence intervals will be determined.

Additional analyses may be performed.

11. Immunogenicity: Anti-SYN023 Antibodies Analyses

Shells for all summary descriptive statistic tables and listings referred to in this section are displayed in a separate document; the shells may be revised as they are presented to illustrate the general layout of data to be included in the final report.

Immunogenicity analyses will be performed on PP population. No inferential analysis will be done.

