### Criteria for Pharmacodynamic Similarity Acceptance

Rabies Virus Neutralizing Activity plotted against time will be created. Pharmacodynamic parameters for SYN023 mAb will be estimated using non-compartmental analysis. Cmax, Tmax, AUC0-last, AUC0-inf will be calculated. For the comparison of RIG to SYN023 with RVi and RVa vaccines: The 90% confidence intervals for the ratio of geometric means (RIG/SYN023) must be 80% to 125%. An ANOVA of the ln-transformed AUC0-inf will be run to determine the 90% confidence interval on the difference between treatments. The confidence interval limits derived on the log scale will be back-transformed to the raw AUC scale for comparison to the acceptance criteria.

To investigate any interference of SYN023 to the immune response generated by the vaccine, a non-inferiority test of the AUC14-last between RIG and SYN023 for each vaccine can be performed. The one-sided 90% confidence interval derived on the log transformed AUC from an ANOVA would be compared to the lower acceptance criterion of 80%.

Additionally, a non-inferiority test of the level of RVNA between RIG and SYN023 for each vaccine at selected time points, such as 14 or 28 days, can be performed using a Wilcoxon rank sum approach with a non-inferiority of 10% of the level associated with RIG. Pharmacodynamic efficacy will be defined as RVNA measured above 0.5 IU/mL with RVi and RVa for the duration of the trial and no more than 10% lower for SYN023 compared to RIG at any time point through Study Day 35.

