### **7.7 Sample Size Considerations**

The sample size for this Phase 2 study was selected based on requirement to consider noninferiority of the efficacy parameter, RVNA. The power analysis was performed in SAS 9.2 using the power procedure for noninferiority testing under the assumption of the sample size of 40 per group and likely margin corresponding to SYN023 being no less than 10% lower than RIG. Based on earlier studies, the mean RVNA for 0.3 mg/kg SYN023 of 20 with CV of 15-25% are reasonable. For assumed underlying differences of 0 to 1 IU/mL, there is over 80% to conclude non-inferiority of RVNA level at a specified time point. The sample size of 40 per treatment group should be sufficient to address the efficacy objectives of the study.

The assumptions that a difference of 2 or less is considered unimportant (the approximate mean value for 0.3mg/kg SYN023 of 20 was used), with the range in mean difference from -1 to 1, standard deviation of 3 and power of 0.8, the required sample size of 29 is needed to declare that the new treatment (SYN023) is not more tolerably inferior to the previous treatment (RIG). Also, the power analysis was performed for the sample size of 40, standard deviation 3 and the mean difference of 2. This resulted in the power of 0.838. The above results from the sample size and power analysis showed that the sample size of 40 should be sufficiently powered for this study.

Also, a power analysis for non-inferiority of the AUCs was performed using “PowerTOST”, an R CRAN package run under Rstudio version 0.99.491. Under the assumption of a lower non-inferiority bound of 0.9 (corresponding to SYN023 being no less than 10% lower than RIG), the selected sample size of 40 per group would provide over 80% power assuming a CV of 10-20%.

If no SAEs are observed among subjects in each dose group and the 40 subjects in the 3 dose groups combined, the one-sided exact upper 95% confidence bounds on the rate of SAE occurrence will be 45% and 18%, respectively.

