10.4.1 Similarity Acceptance

Using GLM procedures in SAS[®], ANOVA will be performed on untransformed $T_{\max,E}$ and ln-transformed $AUEC_{0-t}$, $AUEC_{0-7}$, $AUEC_{0-14}$, $AUEC_{14-t}$, $AUEC_{14-35}$, and E_{\max} at the alpha level of 0.05. Factors incorporated in the model will include: Vaccine, IG, and Vaccine*IG. Vaccine, IG, and Vaccine*IG will be tested against the residual mean square error. In the case of a non-statistically significant Vaccine*IG interaction term, the analysis will be rerun excluding this term from the ANOVA model in order to obtain ratios and confidence intervals where appropriate. In the case of statistically significant Vaccine*IG interaction term, the analysis will be rerun for each vaccine separately. All sums of squares (Types I, II, III and IV) will be reported. Probability (p) values will be derived from Type III sums of squares. Coefficients of variation (CV%) will be estimated.

Based on pairwise comparisons of the ln-transformed $AUEC_{0-t}$, $AUEC_{14-t}$, and E_{\max} data, the ratio (RIG/SYN023) of the geometric least-squares means, calculated according to the formula “ $e^{(X-Y)} * 100$ ”, as well as the corresponding 90% geometric confidence intervals will be determined.

For $AUEC_{14-t}$, a statistically significant Vaccine*Conmed interaction term will be interpreted as a possible interference of RIG or SYN023 on the vaccines. In this case, each vaccine will be investigated separately.

Additional analyses may be performed.

Criteria for Similarity

Considering PP population, the 90% geometric confidence intervals of the ratio (RIG/SYN023) of least-squares means from the ANOVA of the ln-transformed $AUEC_{0-t}$ must be within 80.00% to 125.00%.

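### Protocol 7.7 gives no alpha, and no single alpha reproduces both its n of 29 and its power of 0.838; SAP 10.4.2 likewise leaves open which interval level would be read

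*SAP*

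**What the plan says.** Protocol 7.7 describes the basis of the calculation: "The power analysis was performed in SAS 9.2 using the power procedure for noninferiority testing under the assumption of the sample size of 40". The 40 is a group size. It takes a mean RVNA of 20, a CV of 15-25% and a margin of 10%, that is 2 IU/mL. For true differences from -1 to 1, SD 3 and power 0.8, it concludes that "the required sample size of 29 is needed to declare that the new treatment (SYN023) is not more tolerably inferior" to RIG. It then adds: "the power analysis was performed for the sample size of 40, standard deviation 3 and the mean difference of 2. This resulted in the power", and gives the value 0.838. Neither figure comes with an alpha or a statement of sidedness.

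Protocol 7.3 says that a non-inferiority test for each vaccine at selected time points "can be performed using a Wilcoxon rank sum approach with a non-inferiority of 10% of the level associated with RIG". It also defines pharmacodynamic efficacy partly as RVNA "no more than 10% lower for SYN023 compared to RIG at any time point through Study Day 35". No confidence level is attached to either.

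SAP 10.4.2 fits a separate ANOVA to ln-transformed RVNA on each of nine days, ending "Day 35, Day 42, Day 84, and Day 112 at the alpha level of 0.05". It drops a non-significant vaccine interaction, and analyses each vaccine separately only if the interaction is significant. For the RIG/SYN023 ratio it reports the estimate "as well as the corresponding 90% and 95% geometric confidence intervals will be determined". It gives no margin and does not say which interval is decisive. SAP 10.4.1, by contrast, requires "the 90% geometric confidence intervals of the ratio (RIG/SYN023) of least-squares means from the ANOVA of the ln-transformed" AUEC0-t to lie within 80.00% to 125.00%: one level with one pair of limits.

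**The concern.** The two figures in 7.7 stand next to each other as support for one conclusion, that 40 per group is enough for time-point non-inferiority. If they come from tests with different error levels, the reader cannot tell what error rate the trial was sized for, and the power quoted for 40 per group does not belong to the test that gave 29.

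The second figure also has a labelling problem. It is given for a mean difference of 2, which is the margin itself. In a non-inferiority test, a true deficit equal to the margin puts the truth on the null boundary, where power equals alpha.

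The SAP could have settled the level, but it reports two. A two-sided 90% interval corresponds to a one-sided 5% non-inferiority test, and a 95% interval to one-sided 2.5%. These are the same two levels that 7.7 mixes.

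**Working it through.** **Inputs.** From Protocol 7.7: SD 3, margin 2, power 0.8, n=40 per group, true difference -1 to 1, CV 15-25%. From Protocol 7.3: 10% limit. From SAP 3.1 and 10.4: 40 per treatment, two-factor model. Assumptions: 29 is per group, there is no dropout, and the difference of 2 given with 0.838 is the distance from the truth to the margin.

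**Method.** Two-sample t-test with equal groups. Power = P(T > t(1-α, 2n-2)), where T is noncentral t with noncentrality δ/(SD·√(2/n)) and δ is the distance from the true difference to the margin.

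**Reproducing the plan's figures, δ=2.** At n=40 the noncentrality is 2/(3·√(2/40)) = 2.981. The critical values on 78 df are 1.665 (one-sided 0.05) and 1.991 (one-sided 0.025).

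| One-sided α | n per group for 80% power | Power at n=40 |
|---|---|---|
| 0.10 | 21 | 0.954 |
| 0.05 | **29** | 0.905 |
| 0.025 | 37 | **0.838** |

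Each stated figure is reproduced, but on a different row. At one-sided 0.05, power is 0.793 with 28 per group and 0.806 with 29, so 29 is exact. A two-sided 5% test to detect a difference of 2 with 40 per group also gives 0.838. Solving backwards, 29 needs a one-sided alpha of about 0.048 to 0.052, and 0.838 needs 0.0251.

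**Other methods tried.**
- Normal approximation: n of 28 with power 0.909 (one-sided 0.05), or 36 with 0.847 (0.025).
- Two one-sided tests at 0.05 with margin ±2: power 0.810 at n=40 (0.819 by normal approximation), but 39 per group are needed.
- Wilcoxon with relative efficiency 0.955: n of 31 with power 0.891 (0.05), or 39 with 0.818 (0.025).

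None gives 29 and 0.838 together.

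**Literal reading of the second figure.** A true deficit of 2 against a margin of 2 gives δ=0, so power is 0.05 or 0.025, not 0.838.

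**Within 7.7's own range.** At a true deficit of 1, δ=1. Power at n=40 is 0.43 (one-sided 0.05) or 0.31 (0.025), and 80% power needs 112 or 143 per group. Both stated figures therefore hold only at zero true difference.

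**Effect of the interval level in SAP 10.4.2, if the 10% rule is read against an interval.** On the log scale σ = √ln(1+CV²), and SE = σ·√(2/n). The smallest SYN023/RIG ratio that passes is 0.9·exp(t·SE). At CV 25%, σ = 0.2462.

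| Model, CV 25% | SE | Smallest passing ratio, 90% vs 95% interval | Pass rate under equality |
|---|---|---|---|
| Pooled over vaccines, 80 vs 80, 157 df | 0.0389 | 0.960 vs 0.972 | 85% vs 77% |
| By vaccine, 40 vs 40, 78 df | 0.0551 | 0.986 vs 1.004 | 60% vs 47% |

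At CV 15% the thresholds are 0.936 vs 0.943 pooled and 0.951 vs 0.962 by vaccine.

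**The case against.** The strongest reply is that SAP 10.4.2 contains no decision to corrupt. It has no margin and no pass/fail rule. The SAP's only acceptance criterion is the single 90% interval for AUEC0-t, and all other PD parameters are secondary. Reporting two intervals for a secondary estimate is not an error in itself. The protocol's 10% rule is not tied to any interval, and could be read on the point estimate. This stands, so the interval part of the point is conditional.

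Three stronger readings are tempting, and the documents do not support them:

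- A reader might infer that the time-point analysis has no error level at all. SAP 10.4.2 does state alpha 0.05 for the ANOVAs and their terms. What it leaves open is the interval level for the ratio.
- A reader might infer that the 95% interval would fail an observed ratio of exactly 1. That happens only at CV 25% with 40 versus 40, which the SAP reaches only after a significant interaction. In the default pooled model the threshold is 0.972. Protocol 7.3 does specify a comparison for each vaccine, but for an optional Wilcoxon test.
- A reader might infer that the level is meant to be picked after the data are seen. Nothing in the documents says so. The plan merely does not rule it out.

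It can also be said that 0.838 was a supplementary difference test, not a second alpha for the same test. That is possible, since the two-sided 5% test gives the same number. But 7.7 offers it as support for the same sizing without saying so, and it is then not a non-inferiority power. Lastly, 40 exceeds both 29 and 37. That is correct: at SD 3 and zero true difference the size suffices at either level.

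**Conclusion.** The point holds for Protocol 7.7 as written. One non-inferiority sizing is supported by two figures that need different alphas: 29 goes with 0.905 at one-sided 0.05, and 0.838 goes with 37 at one-sided 0.025. Neither pair covers the stated range of true differences, because power at n=40 falls to 0.43 or 0.31 at a deficit of 1. The alphas are inferred by matching outputs, since the section gives none. The match assumes n per group and no dropout.

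For SAP 10.4.2 the point is narrower. If the 10% rule is applied to an interval, the level needs naming. The consequence is 8 percentage points of pass rate under equality in the pooled model at CV 25% (85% versus 77%), and 13 points in the by-vaccine fallback (60% versus 47%). The AUEC0-t similarity criterion is not touched.

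**What to change.** In Protocol 7.7, state one alpha with its sidedness and the assumed true difference, and report a matching pair: 29 per group with power 0.905 at n=40 (one-sided 0.05), or 37 per group with power 0.838 (one-sided 0.025). State that the pair holds only at zero true difference with SD 3 and margin 2, and that at a true deficit of 1 the power at n=40 is 0.43 or 0.31 respectively. Remove the description of 0.838 as the power at a mean difference of 2, or label it as a two-sided test to detect that difference.

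In SAP 10.4.2, name the interval that matches the alpha chosen in 7.7 (90% for one-sided 0.05, 95% for one-sided 0.025) as the one read if the protocol's 10% rule is applied to an interval, and label the other descriptive. If both are meant as descriptive, say that instead.

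The cost is wording and a few recomputed figures, with no change to enrolment. The sponsor gives up the choice of interval and has to state less favourable power away from zero difference.

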11.1 Immunogenicity Parameters

A total of 8 blood samples will be drawn from each subject for anti-SYN023 antibodies analyses (anti-CTB011 and anti-CTB012). Blood samples will be collected on Day 0, Day 7, Day 14, Day 28, Day 35, Day 42, Day 84, and Day 112.

A figure presenting the proportion of subjects with positive anti-CTB011 and anti-CTB012 results over time will be provided.

No formal parameter will be calculated.

11.2 Statistical Analyses

For anti-CTB011 and anti-CTB012, the number of subjects (frequency and percentage) will be tabulated for each individual result (e.g. negative or positive)

Additional analyses may be performed.

12. Pharmacokinetic Analyses

Shells for all summary descriptive statistic tables and listings referred to in this section are displayed in a separate document; the shells may be revised as they are presented to illustrate the general layout of data to be included in the final report.

PK analyses will be performed on PP population. No inferential analysis will be done.

12.1 Handling of the BLQ and the No Reportable Concentration Values

All concentration values below the lower limit of quantification (BLQ) will be set to zero. Samples with no reportable value occurring prior to the first dosing will be replaced by “0.00” otherwise they will be set to missing for tabulation, graphical representation and calculation purposes.

12.2 Handling of the Difference Between the Scheduled and the Actual Sampling Times

The actual clock time for dosing and the actual clock time for each collection time for the PK samples will be recorded using the electronic data capture. For all sampling times, the actual sampling times will be calculated as the difference between the sample collection actual clock time and the actual clock time of dosing. The actual post-dose sampling times expressed in

hours and rounded off to three decimal digits will be used to calculate the PK parameters, except for pre-dose samples occurring prior to dosing, which will always be reported as zero (0.000), regardless of the time difference. Scheduled sampling times will be presented in concentration tables and mean graphs, while actual sampling times will be presented in the individual graphs in the PK section of the report. A listing of the actual times for PKs will be provided for PK samples.

12.3 Pharmacokinetic Parameters

A total of 9 blood samples will be drawn from each subject for PK analyses. Blood samples will be collected on Day 0, Day 1, Day 3, Day 7, Day 14, Day 28, Day 35, Day 42, and Day 84.

For subjects receiving Treatment C (RVi + SYN023) or Treatment D (RVa + SYN023), serum concentrations from CTB011 and CTB012 will be used to calculate the following parameters separately by standard non-compartmental methods:

- AUC_{0-t} : area under the concentration-time curve from time zero to the last non-zero concentration, calculated using the linear trapezoidal method. Unit will be Day*ng/mL.
- AUC_{0-inf} : area under the concentration-time curve from time zero to infinity (extrapolated), calculated as $AUC_{0-t} + C_t / K_{el}$, where: C_t = the last observed non-zero concentration. Unit will be Day*ng/mL.
- C_{max} : maximum observed concentration. Unit will be ng/mL.
- T_{max} : time of observed C_{max} . Units will be Day
- $T_{1/2\ el}$: elimination half-life, calculated as $\ln(2) / K_{el}$. Unit will be Day.
- K_{el} : elimination rate constant. This parameter will be the negative of the estimated slope of the linear regression of the ln-transformed concentration versus time profile in the terminal elimination phase. At least 3 concentration points will be used in estimating K_{el} . The actual sampling time where ln-linear K_{el} calculation begins ($K_{el\ Lower}$) and the actual sampling time of the last quantifiable concentration used to estimate the K_{el} ($K_{el\ Upper}$) will be reported with the correlation coefficient from the linear regression to calculate K_{el} (Correlation). Unit will be /Day.
- Clp : Plasma clearance, calculated as $Dose / AUC_{0-inf}$. Units will be L.
- Clp/kg : Plasma clearance normalized for the subject body weight in kg, calculated as $Dose / AUC_{0-inf} / weight$. Units will be L/kg.

The K_{el} , $T_{1/2\ el}$, AUC_{0-inf} , Clp and Clp/kg parameters will not be estimated for serum concentration-time profiles where the terminal linear phase is not clearly defined.

Some PK parameters may not be calculated for all or some subjects, at the discretion of the inVentiv pharmacokineticist, if the concentration data is not deemed to be amenable to

evaluation. Explanations for PK parameters that could not be estimated will be provided in the CSR.

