## 1.2 Description of SYN023

SYN023 is a mixture of two anti-rabies humanized monoclonal IgG1 $\kappa$  antibodies, CTB011 and CTB012, which bind to distinct and non-overlapping antigenic sites on the rabies glycoprotein. N355 and H389 are the critical binding residues for CTB011 and H289, L290 and V291 are the critical residues for CTB012. As with RIG, the goal of treatment with SYN023 is to rapidly establish protective levels of anti-rabies antibody in individuals exposed to the rabies virus. Since RIG is derived from pooled sera of human donors or horses vaccinated against rabies (human rabies immune globulin and equine rabies immune globulin, respectively), there is a limited supply, particularly in endemic areas. Thus, there is an urgent need for improved approaches to the critical initial treatment period. SYN023, a mixture of two anti-rabies humanized monoclonal IgG1 $\kappa$  antibodies, CTB011 and CTB012, has been shown to neutralize more than 15 contemporary clinical isolates of rabies viruses collected in China, and the 10 predominant strains in the US.

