### **3.5.1 SYN023 (Study Drug)**

One or more IM injections of the calculated dose of SYN023 should be administered in any of the acceptable injection sites on the RIGHT side of the body on Study Day 0. If for some reason left sided administrations sites must be used a record must be kept of the site and care taken to not administer SYN023 at a rabies vaccination site. SYN023 is supplied at a concentration of 10 mg/mL. For example a dose calculation for a 70 kg person receiving SYN023 at the dose of 0.3 mg/kg would require a dose of 21mg resulting in a dose volume of 2.1 mL. This would need to be administration into injection sites as described below. A needle no smaller than 21-gauge and 1.0 to 3.0 inches in length depending on subject size should be used to draw up the dose of SYN023. Aspiration of SYN023 from the vial should be done gently to avoid foaming.

SYN023 is to be administered as one or more IM injections in one of three possible injection site: the gluteus medius (ventrogluteal injection site/hip), the vastus lateralis (thigh), rectus femoris (thigh) and the deltoid muscle. Doses of up to 5 mL may be given as a single injection into the hip and thigh muscles. Doses up to 3 mL may be given if required in the deltoid muscle. No more than one injection may be administered into each muscle. Only a single deltoid administration is permitted in any subject. Injections into the gluteus maximus (buttocks) will not be performed.

When selecting the site of injection, known paths of nerves, arteries and veins are to be avoided. If available ultrasound assessment of thickness of fat pad and survey of nerve and blood vessel paths may be employed. The needle should be inserted into the skin at a 90° angle. Before SYN023 is administered, aspirate gently by pulling back on the plunger. If blood is drawn into the syringe, the needle is in a blood vessel and must be moved. Remove the needle from the muscle, re-insert it in a new location in the same muscle, and repeat the aspiration step before administering SYN023. If a dose of SYN023 is drawn up and cannot be administered immediately, the syringe may be stored at 2° to 8° C and used within 3 hours.

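### SAP 12.3 gives clearance in volume units (L and L/kg), and does not say which dose is divided by each antibody's AUC when CTB011 and CTB012 are analysed separately

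*SAP*

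**What the plan says.** Protocol 1.2 describes the product: "SYN023 is a mixture of two anti-rabies humanized monoclonal" antibodies, CTB011 and CTB012. Doses are always stated for the mixture. Protocol 2.2 and SAP 3.3 give 0.3 mg/kg, and the worked example in Protocol 3.5.1 is a 70 kg person who, "receiving SYN023 at the dose of 0.3 mg/kg would require a dose of 21mg". Neither document gives a mixing ratio or a dose for either antibody.

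Protocol 7.5 plans PK parameters, clearance among them, for SYN023 and gives no formula or unit. SAP 12.3 moves to the two components: "serum concentrations from CTB011 and CTB012 will be used to calculate the following parameters separately by standard non-compartmental methods". The relevant entries in its list are:

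- AUC0-inf, where "C_t = the last observed non-zero concentration. Unit will be Day*ng/mL";
- for clearance: "Plasma clearance, calculated as $Dose / AUC_{0-inf}$. Units will be L";
- for the weight-adjusted version, the same quotient divided again by the subject's weight, with L/kg as the unit.

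The word Dose is not defined. SAP 4, which lists changes from the protocol, does not mention the move from one analyte to two. SAP 12.2 adds that actual sampling times in "hours and rounded off to three decimal digits will be used to calculate the PK parameters".

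**The concern.** Two things in the clearance lines do not fit the rest of SAP 12.3.

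First, L and L/kg are the units of a volume of distribution. A clearance needs a time in the denominator, and the AUC unit in the same list supplies one.

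Second, an AUC for one antibody has to be paired with the dose of that antibody. The only dose that a programmer can find in the two documents is total SYN023. Used with a single antibody's AUC, it gives a clearance that is too high.

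Determining the PK of SYN023 is a secondary objective, and clearance is a named parameter in both documents. PK information also goes into the review after Study Day 42, which is meant to inform the choice of dose level, although neither document says that clearance is part of that review. A clearance with the wrong unit and an unstated numerator cannot safely be set beside the Phase 1 results or another antibody's.

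**Working it through.** **Units.** The inputs are the formula and the AUC0-inf unit, both from SAP 12.3.

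- Dose has dimension mass. AUC0-inf, in Day*ng/mL, has dimension mass × time / volume.
- Dose / AUC0-inf = mass ÷ (mass × time / volume) = volume / time.
- In units: ng ÷ (Day*ng/mL) = mL/day, and dividing by 1000 gives L/day. For a dose in mg, 1 mg = 10^6 ng, so 1 mg ÷ (Day*ng/mL) = 10^6 mL/day = 1000 L/day.
- Dividing by weight gives L/day/kg.

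The SAP's L and L/kg cannot be reproduced from its own formula and AUC unit. This needs no assumption.

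**Dose.** The inputs are 0.3 mg/kg and the 70 kg example (0.3 × 70 = 21 mg, as in Protocol 3.5.1). The share f of CTB011 by mass is an assumption, because the documents do not give it.

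- Clearance of CTB011 from its own dose: f × D / AUC(CTB011).
- The same with the total dose: D / AUC(CTB011).
- Ratio of the second to the first: 1/f. For CTB012 it is 1/(1 − f). The AUC cancels, so the ratio depends on f alone. Clp/kg has the same ratio, because both versions are divided by the same weight.

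| Assumed f (CTB011) | CTB011 dose at 70 kg | CTB012 dose at 70 kg | CTB011 ratio | CTB012 ratio |
|---|---|---|---|---|
| 0.3 | 6.3 mg | 14.7 mg | 21/6.3 = 3.33 | 21/14.7 = 1.43 |
| 0.4 | 8.4 mg | 12.6 mg | 21/8.4 = 2.50 | 21/12.6 = 1.67 |
| 0.5 | 10.5 mg | 10.5 mg | 21/10.5 = 2.00 | 21/10.5 = 2.00 |
| 0.6 | 12.6 mg | 8.4 mg | 1.67 | 2.50 |
| 0.7 | 14.7 mg | 6.3 mg | 1.43 | 3.33 |

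Because f and 1 − f add to 1, one of them is at most 0.5. If the total dose were used, at least one antibody's clearance would therefore be overstated by 2.0-fold or more, whatever the mixture.

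**Other ways to fill in Dose.** With each antibody's own dose the ratio is 1.0. With the total dose over the AUC of the summed concentrations, numerator and denominator again match. The result is D ÷ [f × D/CL(CTB011) + (1 − f) × D/CL(CTB012)], which equals the common clearance when the two are equal and otherwise lies between them.

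**Time unit.** SAP 12.2 expresses elapsed time in hours, and SAP 12.3 sets day-based units for AUC, Tmax, half-life and Kel. Dividing hours by 24 satisfies both.

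**The case against.** The strongest reply is that the formula does not say total dose. The SAP analyses each antibody separately by standard methods, and in that setting the natural reading of Dose is the dose of the analyte in hand, which gives no bias. SAP 12.4 supports this: where it needs a SYN023 concentration it adds CTB011 and CTB012, so its authors kept the parts and the whole apart. This stands. A reader might infer that both clearances will come out too high. The documents do not show that; they show an undefined numerator and a bias that depends on how it is filled.

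A reader might also infer a 24-fold error from hours in SAP 12.2 and days in SAP 12.3. That does not hold. One section says how times are recorded and rounded, the other says how results are reported, and an analyst who follows both converts. The same applies to the RVNA areas in SAP 10.2 and 10.3.

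Nor is the label plasma clearance an error in the values. Dosing is intramuscular, so dose over AUC is apparent clearance (Cl/F), but that is a matter of naming. Protocol 1.3 reports bioavailability above 90% in rats and dogs and no human figure, so no numerical harm can be shown.

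Finally, the missing time unit can be recovered from the AUC unit in the same list. That makes the unit error easy to put right, but L and L/kg remain wrong as specified.

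**Conclusion.** The units in SAP 12.3 are wrong as written: Clp should be in L/day and Clp/kg in L/day/kg. This follows from the SAP's own formula and AUC unit.

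The dose for each antibody is unspecified. If total SYN023 were used, the overstatement would be 1/f: 2.0-fold for both antibodies at equal mass, and 1.43- to 3.33-fold over f from 0.3 to 0.7. These figures rest on two assumptions that the documents do not settle, namely that the total dose is entered and what the mixing ratio is. If each antibody's own dose is entered, there is no bias.

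The reach is limited to the absolute values and labels of a secondary PK parameter that is only described, not tested. The primary AUEC0-t comparison does not use clearance. AUC, Cmax, Tmax, Kel and half-life do not involve the dose. In the descriptive comparison of Treatments C and D the factor cancels from the ratio for each antibody, provided both arms receive the same mixture.

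**What to change.** In SAP 12.3:

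- Change the units of Clp to L/day and of Clp/kg to L/day/kg.
- Define Dose for each analyte as the SYN023 dose actually given (mg) times that antibody's mass fraction in the product. Alternatively, report a single SYN023 clearance from the total dose and the AUC of the summed CTB011 and CTB012 concentrations, and say so.

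Optional clarifications, neither of which corrects a value: label the parameters Cl/F and Cl/F per kg, and state in SAP 10.2 and 12.2 that times in hours are converted to days before the parameters are calculated. It would also help to record the move from SYN023 to two analytes in SAP 4.

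The cost is SAP wording plus one figure, the mass fraction, which has to come from the sponsor. The amount given to each subject must also be available to the PK analyst; the administration listing in SAP 8.6 does not name it among its contents. No sample, visit or assay changes.
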